9.5.3.1.4 Relationship to Study Drug

The relationship of the study drug to each AE will be determined by the Investigator based on the following definition:

- No reasonable causal relationship (probably not related): There is no plausible temporal relationship or there is another explanation that unequivocally provides a more plausible explanation for the event.
- Yes, reasonable causal relationship (possibly related): There is evidence in favor of a causal relationship; i.e., there is a plausible time course, and at least one of the following criteria apply:

- There is a reasonable pharmacological relationship (or known class effect)
- There is no other more plausible explanation
- There is a positive de-challenge (without active treatment of the event)
- There is a positive re-challenge
- There is a distinguishable dose effect

Within the reporting requirement under 21 CFR 312.32(c)(1)(i), the FDA provides the following examples of types of evidence that would suggest a causal relationship between the drug and the adverse event.

- A single occurrence of an event that is uncommon and known to be strongly associated with drug exposure (e.g., angioedema, hepatic injury, Stevens-Johnson Syndrome).
- One or more occurrences of an event that is not commonly associated with drug exposure, but is otherwise uncommon in the population exposed to the drug (e.g., tendon rupture).
- An aggregate analysis of specific events observed in a clinical trial (such as known consequences of the underlying disease or condition under investigation or other events that commonly occur in the study population independent of drug therapy) that indicates those events occur more frequently in the drug treatment group than in a concurrent or historical control group.

9.5.3.1.5 Reporting and Documenting SAEs

All SAEs beginning with the time of signing IC and continuing until two weeks after administration of the final dose of study medication must be reported. The following steps will be taken to report promptly and document accurately any SAE, whether or not it appears to be related to the study medication:

- 1) Report the SAE to Med Communications, Inc. **by telephone or fax within 24 hours** after becoming aware that a subject has experienced an SAE (see [Appendix 17.1](#) for contact information).
- 2) Record the SAE accurately in the source documents and on the AE page of the subject's eCRF, as described in [Section 9.5.3.1.2](#). Using the Serious Adverse Event Reporting Form, submit all known subject information to Med Communications, Inc. (as specified in separate instructions provided to the study center) on the SAE reporting form **within 24 hours of learning of the SAE occurrence**.

- 3) Perform appropriate diagnostic tests and therapeutic measures, and submit all follow-up substantiating data, such as diagnostic test reports, hospital discharge summaries, and autopsy report to the Sponsor's representative.
- 4) Respond in a timely manner to any queries from Sponsor regarding the SAE.
- 5) Conduct appropriate consultation and follow-up evaluation until the SAE is resolved, stabilized, or otherwise explained by the Investigator.
- 6) Review each SAE report and evaluate the relationship of the SAE to study treatment. The Sponsor will determine whether the SAE is unexpected in nature.
- 7) The Investigator must report all AEs or SAEs that meet the criteria for Unanticipated Problems Involving Risks to Human Subjects or Others to the IRB.

9.5.3.1.6 Follow-Up of Adverse Events

Any ongoing study drug-related AE present at the time of study termination, including a clinically significant laboratory test abnormality, will be followed until resolved or until the event stabilizes and the overall clinical outcome has been ascertained.

In the event of unexplained, treatment-emergent, clinically significant abnormal laboratory test results or clinically significant changes in laboratory test results, the tests should be repeated immediately and followed until the values have returned to within the reference range or to baseline for that subject.

9.5.3.1.7 Medication Error and Overdose

An overdose is defined as a known deliberate or accidental administration of investigational drug, to, or by a study subject, at a dose above that which is assigned to that individual subject according to the study protocol.

If the subjects/caregivers accidentally administer the wrong dose of study drug, they are to **immediately** contact the site to discuss possible safety concerns and receive instructions regarding future doses. All cases of medication errors and overdose (with or without associated AEs) will be documented on the eCRF in order to capture this important safety information consistently in the database. AEs associated with an overdose and SAEs of overdose are to be reported according to the procedures outlined in [Sections 9.5.3.1.2](#) and [9.5.3.1.5](#), respectively.

In the event of drug overdose, the subject is to be treated.

9.5.3.1.8 Review of Adverse Events and Emerging New Safety Information

The Sponsor's Medical Monitor or designee in Pharmacovigilance will perform an ongoing review of all AEs and all other emerging new information relevant to the safety of the drug.

9.5.3.1.9 Reporting of IND Safety Reports

The sponsor will notify the US FDA and all investigators on any new serious risks associated with the drug.

9.5.3.2 Pregnancy Reporting

All female subjects of childbearing potential will undergo urine pregnancy tests at Baseline/Day 1 (Week 26 of Study HZNP-ACT-301), and Weeks 4, 13, and 26 (or PW) and will be instructed to use effective contraceptive measures in line with the inclusion and exclusion criteria. In case a female subject becomes pregnant during the study observation period (from Baseline to Week 26) or pregnancy is confirmed within 30 days after the final study visit, the Investigator will immediately inform the Sponsor of the clinical trial using the Pregnancy Reporting Form. Pregnant subjects still ongoing in the trial will be withdrawn. Information regarding the outcome of the pregnancy must be provided shortly after the birth of the child or the termination of the pregnancy. Pregnancies will be followed whether or not an AE in the mother or the unborn child has been observed.

Male subjects should refrain from fathering a child or donating sperm during the study and for 30 days following the last dose of study drug. Pregnancy of the subject's partner is not considered to be an AE; however, the outcome of all pregnancies should (if possible) be followed up and documented.

9.5.3.3 Vital Signs

Vital signs (resting systolic and diastolic blood pressure in the non-dominant arm, pulse, and temperature) will be assessed at Baseline/Day 1 (Week 26 of Study HZNP-ACT-301), and Weeks 4, 13, and 26 (or PW). Blood pressure and pulse measurements will be obtained with the subject's arm unconstrained by clothing or other material and while the subject is sitting up. When possible, the same arm will be used for measurements in all study visits. Temperature will be obtained orally or via the ear.

9.5.3.4 Physical Examinations, Height, and Weight

Complete physical examinations (including evaluation of general appearance/mental status, HEENT [head, eyes, ears, nose, throat], and the following body systems: skin, heart, lungs, abdomen, extremities) will be performed at Baseline/Day 1 (Week 26 of Study HZNP-ACT-301), and Weeks 13 and 26 (or PW). Brief physical examinations will be performed at the Week 4 and Follow-Up Safety Visits.

Height and weight will be assessed at Baseline/Day 1 (Week 26 of Study HZNP-ACT-301), and Weeks 4, 13, and 26 (or PW); dosing will be based on the calculated BSA at Baseline/Day 1, and Weeks 4 and 13.

9.5.3.5 Echocardiograms

Echocardiograms are scheduled for Baseline/Day 1 (Week 26 of Study HZNP-ACT-301) and Week 26 (or PW).

9.5.3.6 ECGs

ECGs are scheduled for Baseline/Day 1 (Week 26 of Study HZNP-ACT-301) and Weeks 13 and 26 (or PW).

9.5.3.7 Clinical Laboratory Tests

Samples of blood (9.3 mL; 1.0 mL for hematology, 3.5 mL for chemistry, 3.0 mL discard, and 1.8 mL for PT/INR/aPTT) and urine are scheduled for collection at Baseline/Day 1 (Week 26 of Study HZNP-ACT-301), and Weeks 4, 13, and 26 (or PW). Additional follow-up samples for clinical laboratory testing should be obtained as clinically indicated.

All clinical laboratory testing, with the exception of on-site urine pregnancy tests during the treatment period for females of childbearing potential, will be performed by the central clinical safety laboratory (URMC).

The following clinical laboratory tests will be performed:

- Complete blood count
- PT (and derivation of INR) and aPTT
- Chemistry panel
- Urinalysis

9.5.3.8 Immunogenicity Testing

Individual blood samples (2 mL) for immunogenicity testing will be collected from all subjects at Baseline/Day 1 (Week 26 of Study HZNP-ACT-301), and prior to dosing at Weeks 4, 13, 26 (or PW), and 28. Samples will be collected in red top tubes, centrifuged, and serum will be collected and stored at $\geq -70^{\circ}\text{C}$ at the site until shipment to the central safety laboratory (URMC). URMC will store the samples at $\geq -70^{\circ}\text{C}$ until shipment to Intertek (San Diego, CA) for immunogenicity testing.

If a subject tests positive for anti-drug antibodies (ADA), he/she will be followed until ADA levels revert to baseline.

9.5.4 Appropriateness of Measurements

The study population consists of subjects who completed Study HZNP-ACT-301; this population was well-defined and consistent with the expected target population for whom ACTIMMUNE will be indicated (pediatric and young adult subjects with a FA functional stage of >1 to <5).

The primary efficacy endpoint (change in FARS-mNeuro from Baseline to Week 26) has been agreed upon with the FDA. The measurements used in this study for the primary and secondary endpoints (ADL, FARStot, and T25FW) are established and well-validated endpoints that have been shown to correlate significantly with functional disability in FA patients [Lynch et al, 2006].

9.5.5 Study Procedures

Subjects who provide Informed Consent/Assent and who meet all the entry criteria for participation in this study will be enrolled in the open-label extension study. Subjects may participate in this study for up to 28 consecutive weeks in total. The order and timing of the assessments at each study visit should be followed so that assessments are performed at consistent times relative to dosing at each visit.

9.5.5.1 Baseline/Day 1 (Week 26 of Study HZNP-ACT-301)

The Week 26 Visit from HZNP-ACT-301 will serve as Baseline/Day 1 for this study. At the Baseline Visit, subjects will receive the last dose of the randomized drug from HZNP-ACT-301(ACTIMMUNE or placebo) in a double-blind fashion, and the first dose of study drug for the open-label extension study ($10 \mu\text{g}/\text{m}^2$) will be distributed for administration at home according to the planned TIW dosing schedule. Baseline assessments should be performed in the order presented below to ensure that the neurological tests are performed at approximately the same time on testing days.

- Collect all used, partially used, and unused study medication kits and vials from Study HZNP-ACT-301.
- Obtain signed, written Informed Consent/Assent and permission to use Protected Health Information (in accordance with the Health Insurance Portability and Accountability Act [HIPAA]) for Study HZNP-ACT-302. Refusal to provide this permission excludes an individual from eligibility for study participation. Record date Informed Consent/Assent was given and who conducted the process on the appropriate source documentation.
- Perform review of inclusion/exclusion criteria.
- Collect blood (9.3 mL; 1.0 mL for hematology, 3.5 mL for chemistry, 3.0 mL discard, and 1.8 mL for PT/INR/aPTT) and urine samples from all subjects for safety clinical laboratory values (including urine pregnancy test [if applicable]). The pregnancy test must be negative for those subjects to be eligible for participation in this study.
- Collect blood samples (2 mL) for immunogenicity testing.
- Collect blood samples (1 mL) for frataxin analyses.
- Measure height and weight to calculate dose volume.
- Educate subjects and caregivers on dosing technique and schedule.
- Between approximately 7 to 10 AM, administer the last dose of double-blind study drug for Study HZNP-ACT-301 or supervise administration of the study drug by either the subject or the subject's caregiver and record date/time of dosing.
- Perform physical examination, including vital signs.

- Enquire about AEs and concomitant medications.
- Perform ADL, and Physician's and Patient's Global Assessments.
- Perform echocardiogram.
- Perform ECG.
- Perform vision testing (LCSLC) and auditory testing (LiSN-S) if normal audiogram results at Screening Visit of Study HZNP-ACT-301.
- Perform QOL assessments (PedsQL, SF-36, MFIS).
- Perform functional staging of FA and neurological assessments (FARS, T25FW, 9-HPT) at approximately 4 to 6 hours post-dose.
- Collect buccal samples and muscle biopsies (optional) for frataxin analysis (muscle biopsies, if performed, will be the last activity prior to dosing activities).
- Use CTCC's electronic system to obtain the enrollment number and study drug kit assignment.
- Dispense a 4-week supply of study drug.

Subjects will be discharged from the study center after all of the Study Day 1 procedures have been completed.

9.5.5.2 Week 4

- Collect all used, partially used, and unused study medication kits and vials.
- Collect blood (9.3 mL; 1.0 mL for hematology, 3.5 mL for chemistry, 3.0 mL discard, and 1.8 mL for PT/INR/aPTT) and urine samples from all subjects for safety clinical laboratory values (including urine pregnancy test [if applicable]). The pregnancy test must be negative for those subjects to continue participation in this study.
- Collect blood samples (2 mL) for immunogenicity testing.
- Measure height and weight to calculate dose volume.
- Educate subjects and caregivers on dosing technique and schedule.
- Between approximately 7 to 10 AM, administer study drug or supervise administration of the study drug by either the subject or the subject's caregiver and record date/time of dosing.

- Perform brief physical examination, including vital signs.
- Enquire about AEs and concomitant medication use.
- Dispense a 6- or 9-week supply of study drug, as applicable.

Subjects will be released from the study center after all of the visit procedures have been completed and instructed to return to the clinic at Week 13.

9.5.5.3 Week 13

- Collect all used, partially used, and unused study medication kits and vials.
- Collect blood (9.3 mL; 1.0 mL for hematology, 3.5 mL for chemistry, 3.0 mL discard, and 1.8 mL for PT/INR/aPTT) and urine samples from all subjects for safety clinical laboratory values (including urine pregnancy test [if applicable]). The pregnancy test must be negative for those subjects to continue participation in this study.
- Collect blood samples (2 mL) for immunogenicity testing.
- Collect blood samples (1 mL) for frataxin analyses.
- Measure height and weight to calculate dose volume.
- Educate subjects and caregivers on dosing technique and schedule.
- Between approximately 7 to 10 AM, administer study drug or supervise administration of the study drug by either the subject or the subject's caregiver and record date/time of dosing.
- Perform physical examination, including vital signs.
- Enquire about AEs and concomitant medications.
- Perform ADL and Physician's and Patient's Global Assessments.
- Perform ECG.
- Perform QOL assessments (PedsQL, SF-36, MFIS).
- Perform functional staging of FA and neurological assessments (FARS, T25FW, 9-HPT) at approximately 4 to 6 hours post-dose.
- Collect buccal samples and muscle biopsies (optional) for frataxin analysis.
- Dispense a 6- or 13-week supply of study drug, as applicable.

Subjects will be released from the study center after all of the visit procedures have been completed and instructed to return to the clinic at Week 26.

9.5.5.4 Week 26 (Termination Visit or Premature Withdrawal Visit)

- Collect all used, partially used, and unused study medication kits and vials.
- Collect blood (9.3 mL; 1.0 mL for hematology, 3.5 mL for chemistry, 3.0 mL discard, and 1.8 mL for PT/INR/aPTT) and urine samples from all subjects for safety clinical laboratory values (including urine pregnancy test [if applicable]).
- Collect blood samples (2 mL) for immunogenicity testing.
- Collect blood samples (1 mL) for frataxin analyses.
- Measure height and weight.
- Between approximately 7 to 10 AM, administer study drug or supervise administration of the study drug by either the subject or the subject's caregiver and record date/time of dosing.
- Perform physical examination, including vital signs.
- Enquire about AEs and concomitant medications.
- Perform ADL and Physician's and Patient's Global Assessments.
- Perform echocardiogram.
- Perform ECG.
- Perform Vision testing (LCSLC) and auditory testing (LiSN-S) if audiogram results were normal at Screening Visit of Study HZNP-ACT-301.
- Perform QOL assessments (PedsQL, SF-36, MFIS).
- Perform functional staging of FA and neurological assessments (FARS, T25FW, 9-HPT) at approximately 4 to 6 hours post-dose.
- Collect buccal samples and muscle biopsies (optional) for frataxin analysis.

Subjects will be released from the study center after all of the visit procedures have been completed and instructed to return in approximately two weeks for the Follow-Up Safety Visit.

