- ³ Study drug will be initiated at home following the Baseline/Day 1 visit at 10 $\mu\text{g}/\text{m}^2$ according to the subject's TIW dosing schedule. The planned dose escalation consists of two doses of ACTIMMUNE 10 $\mu\text{g}/\text{m}^2$ in the first week, followed by weekly escalation to 25, 50, and 100 $\mu\text{g}/\text{m}^2$ TIW on Days 8, 15, and 22, respectively; however, the dose may be reduced, interrupted, or held based on tolerability. All subjects are to be on a stable tolerated dose of study drug by Week 13 in order to continue study participation
- ⁴ At the Baseline/Day 1 visit (Week 26 of Study HZNP-ACT-301), subjects will receive the last dose of study drug from the double-blind Study HZNP-ACT-301 (ACTIMMUNE or placebo). The first dose for this open-label extension study (ACTIMMUNE 10 $\mu\text{g}/\text{m}^2$) will be administered at home before bedtime according to the subject's TIW dosing schedule. Dosing at Weeks 4, 13, and 26 will be performed at the clinic. All other doses will be administered at home before bedtime.
- ⁵ Subjects will be given a 4-week supply of study drug prior to clinic discharge at the Baseline/Day 1 Visit (Week 26 of Study HZNP-ACT-301). At the Week 4 and 13 Visits, subjects will be given a 6-week supply of study drug, and additional study drug will be directly shipped to the subjects' homes as needed; if direct shipment is not feasible, subjects may receive a full supply at Weeks 4 and 13 (9-week supply at Week 4 and 13-week supply at Week 13).
- ⁶ Subjects and/or caregivers will be contacted by email or phone to monitor safety and dosing logistics on a weekly basis during the dose-escalation period (from Day 1 through at least Week 4 [or later until a stable tolerated dose is reached]) and on a monthly basis after dose stabilization (from Week 4 or when dose is stabilized) through Week 26.
- ⁷ Functional staging, FARS, T25W, and 9-HPT will be performed at approximately the same time of day at each visit and by the same examiner.
- ⁸ The LiSN-S will only be performed for subjects who had a normal audiogram prior to enrollment in HZNP-ACT-301. The LiSN-S will be performed at the Baseline/Day 1 (Week 26 of Study HZNP-ACT-301) and Week 26 visits.
- ⁹ Muscle biopsies will be optional for each subject, and consent will be signed prior to biopsy collection. Biopsies will be the last efficacy assessment of the day at Weeks 13 and 26.

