9.3.3 Removal of Subjects from Therapy or Assessment

All subjects are free to withdraw from study participation at any time, for any reason, and without prejudice to their further medical care. In addition, the investigator may terminate a subject from the study at any time. The primary reason for discontinuation should be recorded on the case report form using one of the following categories:

- Adverse event. The subject experiences an AE that imposes an unacceptable risk to the subject's health, or the subject is unwilling to continue because of an AE.
- Lack of therapeutic effect. The investigator has determined that study drug administration is not benefitting the subject, and continued participation poses an unacceptable risk to the subject.
- Inclusion/exclusion criteria violation. The investigator discovers that the subject did not meet all of the inclusion/exclusion criteria after study enrollment.
- Protocol noncompliance. The subject has a significant protocol deviation, does not comply with study drug administration schedule, or fails to adhere to other study requirements as stated in the protocol.
- Lost to follow-up. The subject does not return to the clinic for scheduled assessments, and does not respond to the site's attempts to contact the subject.
- Voluntary withdrawal. The subject (or subject's legally acceptable representative) wishes to withdraw from the study. The clinical site should attempt to determine the underlying reason for the voluntary withdrawal and document it on the eCRF; if the underlying reason is documented as an AE or lack of efficacy, the category of withdrawal should be marked in the corresponding category and not as voluntary withdrawal.
- Study termination. The Sponsor, DSMB, IRB, or regulatory agency terminates the study.
- Pregnancy.

Following early discontinuation from the study, the subject or his/her legally acceptable representative will be informed regarding the additional study evaluations that are necessary to monitor his/her safety. These subjects or their representatives will be encouraged to complete the PW and Follow-Up Safety Visits.

Discontinued or withdrawn subjects will not be replaced. Subject identification numbers are unique and will not be reassigned.

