After Baseline/Day 1 (Week 26 of Study HZNP-ACT-301), subjects are scheduled to return to the clinic at Weeks 4, 13, and 26 during the treatment period. Study drug will be administered in the morning at the clinic at each of these visits. If the subject's next scheduled dose is the same day as the clinic visit, the dose will simply be given in the morning as opposed to bedtime for that particular day. If the subject is scheduled to dose the evening prior to the visit, the dose will be held and administered the next morning at the clinic. Bedtime dosing will be resumed after the clinic visit according to the subject's regular dosing schedule. For the TIW schedule, dosing should be Monday, Wednesday and Friday or alternatively Tuesday, Thursday and Saturday.

At Baseline/Day 1 (Week 26 of Study HZNP-ACT-301), subjects will be dispensed a 4-week supply of study drug for the dose-escalation period (up to 6 kits), and at Weeks 4 and 13, subjects and/or their caregivers will be dispensed a 6-week supply of study drug (up to 12 kits). Additional kits will be shipped to the subject's house between Weeks 4 and 13, and between Weeks 13 and 26, as needed. Subjects/caregivers may be dispensed the full supply at Weeks 4 and 13 if interim direct-to-subject shipments are not feasible. At Weeks 4, 13, and 26, subjects and/or their caregivers will return all unused kits and study drug vials.

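### Protocol Section 9.5.5.4 directs a study-drug dose at the Premature Withdrawal visit, with no exception for subjects withdrawn for an adverse event or pregnancy

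*Protocol*

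**What the plan says.** Section 9.5.5.4 of the protocol covers the Week 26 visit and the PW visit with a single list. After the blood and urine collection, it says: "Between approximately 7 to 10 AM, administer study drug or supervise administration of the study drug". No reason for withdrawal is exempted. The urine pregnancy test is part of the earlier collection step, but the list attaches no consequence to a positive result.

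Section 9.5.5 asks sites to keep to the listed order and timing, so that assessments fall at consistent times relative to dosing.

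Section 9.3.3 lists eight reasons for discontinuation. One is an adverse event, defined in part as: "The subject experiences an AE that imposes an unacceptable risk" to the subject's health. Another is pregnancy. The same section then says: "These subjects or their representatives will be encouraged to complete the PW and Follow-Up Safety Visits". Section 9.5.3.2 requires that a subject who becomes pregnant be withdrawn.

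For comparison, the Week 4 and Week 13 lists (Sections 9.5.5.2 and 9.5.5.3) add after the same test: "The pregnancy test must be negative for those subjects to continue participation in this study".

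**The concern.** Some subjects come to the PW visit because they should not receive more drug, and the list they meet there contains a dose. In the listed order the dose comes before the physical examination, vital signs, adverse-event enquiry, echocardiogram and ECG, so the checks that might stop it come afterwards.

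The hazard is described in the label appended as Section 17.2. The drug is contraindicated once a patient develops hypersensitivity (label section 4), it is to be stopped at once after an acute reaction (label section 5.5), and in pregnancy it is reserved for cases where benefit justifies the fetal risk (label section 8.1). Label section 2.3 also advises against doses above 50 µg/m², while this study titrates to 100 µg/m². Section 9.2 acknowledges that the safety profile of that dose in children with this disease is not known.

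Safety is the study's primary objective, and many participants are minors. Protection of a withdrawn subject should not depend on staff departing from the written procedure.

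**Working it through.** No sample size, power or error rate is involved. The check is whether the protocol plans a dose at PW, and whether any text removes it for the subjects at risk.

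1. **Is a PW dose planned?**
   - Section 9.5.5.4 has the dosing step in the shared list.
   - In Section 2.1, the row for a dose given at the visit is empty at Baseline and marked in the three treatment columns that follow. The last of these is headed Week 26 (or PW).
   - The synopsis and Section 9.1 place the neurological tests four to six hours after a dose at Week 13 and at Week 26 or PW.
   - Section 9.5.1.8 calls the PW frataxin sample post-dose, and Section 9.5.3.8 takes the PW immunogenicity sample before dosing. These two carry less weight because the wording is loose: Section 9.5.3.8 treats Week 28 the same way although no dose is given then, and Section 9.5.5.4 draws frataxin blood before the dose.
   - Together, these texts agree that a dose is planned at PW.

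2. **Do subjects at risk reach this visit?** Yes. Section 9.3.3 encourages withdrawn subjects to attend whatever the reason. Two of the eight reasons are clear hazards: an adverse event and pregnancy.

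3. **Does anything remove the dose for them?**
   - Section 9.1 allows doses to be lowered, paused or withheld for poor tolerability.
   - Section 9.4.1.1 covers severe reactions during escalation, and case-by-case reductions after Week 13.
   - Section 9.5.3.2 withdraws pregnant subjects, which leads to the PW list.
   - None of these says that the PW dose is omitted.

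4. **Does the pregnancy test control the dose?** No. The test is listed before the dose, but no instruction links the two.

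5. **Exposure if the list is followed.** One dose, at the level the subject had reached. Dose in µg = level (µg/m²) × body surface area (m²). With the worked example of 1.41 m² in Section 9.4.7.2:
   - 10 × 1.41 = 14.1 µg
   - 25 × 1.41 = 35.25 µg
   - 50 × 1.41 = 70.5 µg
   - 100 × 1.41 = 141 µg

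   These figures describe the size of the dose. They say nothing about the probability of harm.

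**The case against.** The strongest defence is that a visit checklist does not override the general rules. The dose can be withheld for tolerability, the investigator may end a subject's participation at any time, pregnant subjects are withdrawn, and the protocol refers readers to the label for the safety profile. Section 9.3.3 also describes what follows discontinuation as "additional study evaluations that are necessary to monitor his/her safety". Harm would require a site to re-dose someone it had just removed for a dangerous reaction or a positive pregnancy test. This defence stands as to likelihood. It does not remove the gap, because none of that text mentions dosing at PW and the one list that does says to dose.

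A reader might infer that the protocol contradicts itself on PW dosing. Footnote 4 of the schedule says "Dosing at Weeks 4, 13, and 26 will be performed at the clinic", and Section 9.4.7.3, referring to the same weeks, says "Study drug will be administered in the morning at the clinic at each of these visits"; neither names PW. The documents do not support that inference. Both texts are silent on PW and do not forbid a dose there. The schedule's footnotes drop PW elsewhere as shorthand: footnotes 2, 8 and 9 omit it for height and weight, the auditory test and biopsies, while Sections 9.5.3.4, 9.5.1.7 and 9.5.1.8 include it.

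A reader might also infer that a dosing safeguard used at other visits was dropped at Week 26. That goes too far. The Baseline sentence, "The pregnancy test must be negative for those subjects to be eligible for participation in this study", governs entry, and the clinic dose that day belongs to Study HZNP-ACT-301. The Week 4 and Week 13 sentence governs continuing in the study. At the final treatment visit there is no continuation to condition, so its absence is natural. What remains is narrower: a dose follows the test, and nothing makes it depend on the result.

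**Conclusion.** The point holds as a safety gap in the wording. The protocol plans a dose at PW and makes no exception for subjects withdrawn for an adverse event of unacceptable risk or for pregnancy. It also makes no dose at that visit conditional on the pregnancy test.

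The exposure is one extra dose, 14.1 to 141 µg at the example body surface area. It occurs only if the subject attends, was withdrawn for such a reason, and the site follows the list without using its discretion. The documents give neither the number of PW visits nor any basis for estimating how often this would happen, and an investigator would probably hold the dose. The documents therefore do not support a claim that subjects were or will be harmed.

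The effect on the results is small. SAP Section 8 states that there is no efficacy analysis, the safety summaries are descriptive, and laboratory and immunogenicity blood is listed before the dose. Priority is low to moderate: the chance of harm is low, but the remedy costs very little.

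**What to change.** Amend Section 9.5.5.4, and the schedule row for the dose given at the visit in the Week 26 (or PW) column, so that:

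- the clinic dose is given only to subjects still on treatment at Week 26 and, where applicable, only after a negative on-site urine pregnancy test;
- no study drug is given at PW to a subject who has stopped it, in particular for an adverse event or pregnancy;
- PW assessments, including the neurological tests, are done without reference to dosing.

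The Follow-Up Safety Visit needs no new rule, because the synopsis and Sections 9.5.3.1.2 and 9.5.5.5 already count from the last dose. The closing sentence of Section 9.5.5.4, which asks subjects to return about two weeks later, could be aligned in the same edit.

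The cost is a wording amendment and the loss of post-dose timing for PW assessments. For the neurological tests this matters little, since efficacy will not be analysed. SAP Section 6.1 assigns PW data to the nearest scheduled visit, so a few undosed PW vital signs and ECGs would be summarised with values taken after a dose; a footnote to those tables would be enough. No visit or test is added, because the urine test is already done on site and listed before the dose. Whether the case report form needs a change cannot be judged, as it is not among the documents.
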